**Cystic Fibrosis Foundation**

**Background:** The life span of patients with Cystic fibrosis (CF) continues to be shortened by progressive lung disease. CF can be caused by ~2000 mutations in the cystic fibrosis transmembrane conductance regulator (CFTR) gene. These mutations can be, even though imperfectly, classified into 5 groups, permitting the development of small molecules that rescue group-specific CFTR mutants. These small molecules made remarkable impacts on patients. The CFTR potentiator ivacaftor (Kalydeco™), approved by the FDA mainly for class III mutations, has shown improvements in ion transport (large decrease in sweat chloride), clinical outcome (increase in FEV1 and weight, decrease in exacerbation rates), and quality of life (1). However, ivacaftor did not immediately eliminate airway inflammation, despite improvement in CFTR conductance, at least not within 12 month (2). Later time points may indicate anti-inflammatory effects. *However, airway inflammation is associated with morbidity in CF (reviewed in 3) and additional anti-inflammatory treatment options are needed.*

F508del, a class II mutation, is the most common mutation in the US CF population. The FDA recently approved Orkambi™ and Symdeco™, both combinations of a corrector and potentiator (lumacaftor/tezacaftor and ivacaftor), to reduce exacerbations in F508del homozygous patients. However the effect of both medications on lung function and sweat chloride was modest at best (4-6). One explanation for this suboptimal efficacy *in vivo* could be the ongoing airway inflammation as outlined above. In this context, TGF- $\beta$ 1 has been identified as a disease modifier in CF (7). Increased production of TGF- $\beta$ 1 is common in CF airways and has been associated with worse pulmonary outcome (8,9). In particular, TGF- $\beta$ 1 has been shown to decrease the ability of lumacaftor to rescue CFTR function and airway surface liquid (ASL) volume *in vitro* (10,11). Since tezacaftor has a similar mode of action compared to lumacaftor, it is not surprising that TGF- $\beta$ 1 also decreases the ability of tezacaftor to rescue CFTR currents *in vitro* (our own published observations). TGF- $\beta$ 1-associated inflammation also decreases the function of other ion channels important for ASL volume regulation: Calcium activated chloride channels (CaCC) and the apical potassium channel BK (11,12). We therefore propose that *airway inflammation, especially via TGF- $\beta$ 1, leads to a lower CaCC and BK activity, worsening mucociliary dysfunction in CF. Importantly, TGF- $\beta$ 1 also causes a decreased ability of lumacaftor to rescue F508del CFTR to the membrane, explaining at least part of the suboptimal efficacy of correctors in inflamed airways.*

#### IN VIVO PRELIMINARY EVIDENCE FOR THE ABILITY OF LOSARTAN TO REVERSE MUCOCILIARY DYSFUNCTION IN SHEEP

We developed a large animal model, at least in part simulating CF airway disease by exposing sheep to an inhalation challenge with CFTRinh172 and human neutrophil elastase (HNE) or TGF- $\beta$ 1 (to produce inflammation). Either combination led to a significant reduction in tracheal mucus velocity (TMV), a surrogate marker of mucociliary clearance. Importantly, inhaled losartan reversed the CFTRinh172+HNE- or CFTRinh172+ TGF- $\beta$ 1-induced mucociliary dysfunction *in vivo* (Fig. 1).

**Figure 1.** Effects of losartan on a 3-day challenge model of mucociliary dysfunction. Left: 3-day challenge with CFTRinh172 (10 mg) and HNE (2380 mU) leads to prolonged (at least lasting 48h) mucociliary dysfunction (reduction in TMV) in sheep. Inhaled losartan (50 mg) reversed TMV decreases (solvent of losartan had no effect). Right: Challenge with CFTRinh172 and TGF- $\beta$ 1 (25  $\mu$ g) reduces TMV that is again rescued by inhaled losartan (50 mg). All n = 3. Mean  $\pm$  SE are shown.

#### ADDITIONAL PRELIMINARY DATA

Additional preliminary data in patients show that Orkambi™ alone does not improve CFTR function *in vivo* as measured by nasal potential difference (NPD), possibly because of ongoing inflammation in CF patients. Given the small changes in sweat chloride, the same is true for Symdeco™. *In vitro* data show that:

- Losartan reverses the detrimental effects of TGF- $\beta$ 1 on ASL volume
- Losartan reverses the detrimental effects of TGF- $\beta$ 1 on CaCC and BK currents
- Losartan reverses the detrimental effects of TGF- $\beta$ 1 on lumacaftor-mediated F508del CFTR current recovery
- TGF- $\beta$ 1 has detrimental effects on tezacaftor-mediated F508del CFTR current recovery
- Decreases in ATP-induced PD are a measure of both CaCC and BK dysfunction.

- Losartan improved mucociliary dysfunction in a sheep model with CFTR inhibition and airway inflammation

These data make a compelling case for testing losartan as an anti-inflammatory medication in patients homozygous for F508del to improve the effects of Orkambi™ or Symdeco™ therapy on ion transport. Losartan will be given at least 12 weeks to assure that possible anti-inflammatory effects will have a chance to change the airway environment, since 4 weeks of treatment was insufficient in previous trials with other anti-inflammatory medications.

## Study Design and Methods

**We propose to conduct a proof of concept clinical trial to test if administration of losartan augments CFTR function *in vivo* in patients who are on Orkambi™ or Symdeco™.** The goal of our pilot clinical trial is to examine the ability of losartan on CFTR (primary hypothesis) and possibly BK rescue/augmentation (secondary hypothesis) in patients homozygous for F508del on Orkambi™ or Symdeco™ therapy. The additional benefit for BK channels could be important but is harder to measure *in vivo*. Towards this end, however, we will assess CaCC/BK activity together as the response to ATP during NPD measurements, even though this is not an accurate reflection of either channel on its own.

**Note that ATP-induced changes in NPD in CF patients are higher than in normal subjects because *in vitro* data show that this response is increased in the *absence* of BK activity. Thus, the expectation here is that the rescue of BK activity with losartan will *DECREASE* NPD responses to ATP.**

**Primary hypothesis:** Losartan treatment for 12 weeks will improve CFTR conductance as measured by NPD in patients on Orkambi or Symdeco therapy. We expect that compared to placebo,  $\Delta$ NPD in response to 0 Cl/isoproterenol will change by more than -4 mV using the most polarized nostril each time.

**Secondary hypotheses:** Losartan treatment for 12 weeks will improve BK and CaCC activity as assessed by a decrease of changes in NPD to ATP exposure. Furthermore, losartan will reduce nasal cytokine levels and systemic inflammatory markers.

**Study plan:** Details are seen in Figure 2 and the study table. Briefly, 36 patients with CF, > 12 years of age, who are homozygous for F508del and have been on treatment with Orkambi™ or Symdeco™ for at least 3 months will be recruited for this trial. This trial will be randomized 1:1 with placebo (n=18 for each group). After signing informed consent at the screening visit, we will perform spirometry, determine sweat chloride, take blood (see below), and test for pregnancy where applicable. Since losartan has teratogenic effects, we will enforce strict birth control in female participants (see Potential Risk section.)

Eligible patients will complete visits as outlined below. Quality of life will be assessed by CFQ-R (CF quality of life questionnaire - revised, 13). NPD will use standard protocols and so will nasal cell harvest (see below for assessments). Cytokines will be measured from nasal fluid recovered by Leukosorb filter paper (14). There will be two visits for these different nasal assessments to assure that nasal cell fluid and cell collection will not influence NPD and vice versa. After assessing baselines, a daily dose of 50 mg losartan or placebo will be started. If patient's weight is less than 55 kg dose will be adjusted to a daily dose of 25 mg losartan or placebo. A safety follow up phone call will occur after 7 days of treatment ( $\pm$  2 days) and the losartan dose (or placebo) increased to 25 mg or 50 mg twice a day as higher dose is likely needed to get anti-inflammatory effect in airways if present. Since this trial assesses anti-inflammatory effects of losartan (and lack of placebo), the total duration will be 14 weeks to achieve at least 12 weeks of treatment with the higher dose of losartan (or placebo).

### Endpoints

- Primary endpoint
  - $\Delta$ NPD with 0 Cl/isoproterenol as a measure of CFTR activity in losartan treatment compared to placebo (15), done according to standard procedures (16); for power calculation, see below. All traces will be read blinded at the Cincinnati Children's Hospital Medical Center and University of Alabama at Birmingham for the active or placebo arm.
- Secondary endpoints
  - CaCC and BK activity as measured by change in NPD upon ATP application (see above).
  - Change in sweat chloride concentration
  - FEV1 (absolute and relative changes)
  - Changes in serum inflammatory markers (hsCRP, WBC including absolute neutrophil count, % PMNs, SAA, calprotectin, GM-CSF, TGF- $\beta$  active and total)
  - Nasal cytokine changes (IL-1 $\beta$ , TGF- $\beta$  active and total, IL-6, IL-8 IL-13)
  - Quality of life questionnaire (CFQ-R)
  - Blood levels of losartan, EXP3179, and EXP3174 (17,18)
  - LRRC26 mRNA (correlates with BK activity *in vitro*) and TGF- $\beta$  mRNA expression in nasal cells by qPCR (while some contamination with other cells is possible, "purification" with for instance cell sorting

is not feasible given the small number of cells; we will assess purity after cytopsin with epithelial and other cell markers using immunofluorescence).

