## **STATISTICS AND POWER ANALYSIS**

**Randomization:** Upon eligibility, a statistician randomizes all subjects in a 1:1 ratio to the placebo or losartan treatment group and informs the research pharmacy. Participants will be stratified by site during randomization.

**Design:** The basic study design consists of random assignment of patients to one of two treatment arms: losartan or placebo. Data will be collected at the visits as outlined above.

**Analysis:** Primary endpoint: A t-test will be used as preliminary data analysis. For the formal analysis, mixed effects models model will be used for analysis to accommodate the paired measures nature of the design, as well as missing values under the MAR assumption. We will determine the final analytic approach based on the final available data. Examination of baseline differences on key variables between subjects remaining and those lost-to-follow-up will also be conducted. The first set of analyses will not adjust for dropouts. Only cases with complete data will be included.

Secondary endpoints: Prior to analysis, we will investigate the distributional properties of the defined outcome measures - such as CaCC/BK activity, change in sweat chloride concentration, FEV1, changes in serum inflammatory markers, etc. Necessary transformations such as logarithmic or square root will be applied to satisfy normality assumptions if necessary. Baseline values of all variables will be examined, and estimates of baseline means and changes over time will be provided. The statistical analysis will consist of descriptive statistics associated with outcome measure (mean change or mean difference pre and post treatment) for two treatments. Means at baseline, 6 and 13/14 weeks, for each outcome, as well as the change over time will be provided, as well as the corresponding estimates of variability, and 95% confidence intervals will be constructed. t-tests for comparisons of the changes over the period between treatments will be conducted. However, the primary focus for this analysis is to obtain reliable estimates of the mean changes and variability, which will be useful for designing further investigation focused and specifically powered for comparing these outcomes. P-value will be significant if  $< 0.05$ . All tests will be two-tailed. The SAS statistical software package version 9.3 (Cary, NC) will be used for all statistical analyses.

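### The plan does not say how the Visit 1 NPD enters the primary comparison; several analyses fit the wording, and adjusting for Visit 1 would settle it at almost no cost

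*Combined protocol and SAP*

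**What the plan says.** **Hypothesis (Study Design and Methods).** "Losartan treatment for 12 weeks will improve CFTR conductance as measured by NPD" in patients on a corrector-potentiator combination. Compared with placebo, the response to 0 Cl-/isoproterenol "will change by more than -4 mV using the most polarized nostril each time".

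**Endpoint list (Endpoints).** The primary endpoint is the NPD response to 0 Cl-/isoproterenol "as a measure of CFTR activity in losartan treatment compared to placebo (15), done according to standard procedures (16"). No baseline and no visit are named. Some secondary endpoints in the same list are worded as changes, for example "Change in sweat chloride concentration"; others are not.

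**Analysis (Statistics and Power Analysis).** For the primary endpoint, "A t-test will be used as preliminary data analysis". The variable to be tested is not named. For the formal analysis, "mixed effects models model will be used for analysis to accommodate the paired measures nature of the design". The outcome vector, the role of the pre-treatment value and the contrast are not given. The section then says that the final approach will be decided from the data finally available. For the secondary endpoints, by contrast, it does specify t-tests on changes.

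**Schedule (Appendix 1).** NPD is marked at Visits 1, 5 and 7, so every patient is due one pre-treatment and two on-treatment measurements.

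**The concern.** The NPD response is already a within-session difference: the voltage shift when the perfusate is switched. A statement that it will change after treatment therefore reads most naturally as a second difference, Visit 7 minus Visit 1. The endpoint list can equally be read as the on-treatment response compared between arms. The statistics section does not choose between them.

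Under randomisation both readings target the same mean difference, so this is not a question of bias. But they give different estimates and standard errors in any one dataset. The final value carries all the between-patient spread in the response and ignores Visit 1. The change score subtracts Visit 1 with a slope fixed at 1, so it carries the noise of two tests. A mixed model with Visit 1 as a repeated outcome and free arm means at baseline reproduces the change score through its arm-by-time contrast when data are complete.

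With 18 patients per arm, the choice could decide whether the primary result is significant. As written, the choice can be made after the data are seen.

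**Working it through.** **Inputs from the documents.** Group size: "This trial will be randomized 1:1 with placebo (n=18 for each group"). Effect: 4 mV in absolute size. Significance: "P-value will be significant if" below 0.05, two-tailed.

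**Inputs not in the text.** The SD *s* of the response, the correlation *r* between repeat tests, and the target power. The endpoint list points to a power calculation further on, but none appears in the supplied text. It may have been lost in extraction. So *s* and *r* are assumptions, with equal SD before and on treatment.

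**1. The plan's own figure.** The 36 patients cannot be reproduced without an SD and a power. Solving backwards (two-sample t, 34 df), 18 per arm detects 4 mV with 80% power if the SD of the compared quantity is 4.16 mV, and with 90% power if it is 3.60 mV. The text does not say whether that quantity is a response or a change.

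**2. Standard errors.** SE of the arm difference = SD of the compared quantity × √(2/18) = SD × 0.333. The SDs are:
- final value: *s*
- change: *s*√(2(1−*r*))
- adjusted for Visit 1: *s*√(1−*r*²)

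At *s* = 5 mV the final-value SE is 1.67 mV. For *r* = 0.2, 0.5 and 0.8:
- change: SD 6.32, 5.00, 3.16; SE 2.11, 1.67, 1.05 mV
- adjusted: SD 4.90, 4.33, 3.00; SE 1.63, 1.44, 1.00 mV

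**3. Power for 4 mV, 18 per arm.** Final value and change use the noncentral t distribution. Adjusted figures come from simulated ANCOVA, because the formula in step 2 omits the variance from chance baseline imbalance. At *s* = 5 that formula would give 66%, 77% and 97%.

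| *s* (mV) | Final value | Change, *r* = 0.2 / 0.5 / 0.8 | Adjusted, *r* = 0.2 / 0.5 / 0.8 |
|---|---|---|---|
| 4 | 83% | 63% / 83% / near 100% | 83% / 91% / near 100% |
| 5 | 65% | 45% / 65% / 96% | 65% / 76% / 97% |
| 6 | 49% | 34% / 49% / 87% | 50% / 60% / 89% |

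Final value and change have equal power at *r* = 0.5. The change score is weaker below that and stronger above it. The gain from adjustment over the final value is negligible at *r* = 0.2. At *r* = 0.1 and *s* = 5 it is a small loss (63.6% against 64.5%).

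**4. Disagreement within one trial.** The two estimates differ by exactly the chance arm difference at Visit 1. At *s* = 5 its SE is 1.67 mV, so the mean absolute gap is 1.67 × √(2/π) = 1.3 mV. The gap exceeds 2 mV with probability 2(1−Φ(2/1.67)) = 2(1−Φ(1.2)) = 23%. In simulation with a true 4 mV effect, the two t-tests fall on opposite sides of p = 0.05 in 32%, 31% and 35% of trials at *r* = 0.2, 0.5 and 0.8. At *r* = 0.5 this happens although power is equal. Over *s* = 4 to 6 the range is about 17% to 45%.

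**5. Type I error.** With no effect, at least one of the two t-tests is significant in 8.8%, 9.2% and 9.4% of trials at *s* = 5 for the same three values of *r*, against a nominal 5%.

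**The case against.** A reader might infer that the hypothesis and the endpoint list define two different endpoints. The documents do not support that. The endpoint list is silent on baseline; it does not define a final-value endpoint. The hypothesis can itself be read as a between-arm difference. The contrast with secondary endpoints worded as changes is weak, because quality of life, drug levels and mRNA expression in the same list are not worded that way either.

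A reader might also infer that the plan cannot use Visit 1 efficiently. That goes too far. The t-test is only preliminary. The formal model is meant for paired measures, which leans towards using the pre-treatment NPD. With Visit 1 as a covariate, or with baseline means constrained equal, that model would be about as efficient as ANCOVA. The defect is that it is not specified.

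Nor do the two readings always differ in power: at *r* = 0.5 they do not. Without an SD or a correlation, neither the size nor the direction of a gap is known. A power calculation missing from the supplied text might show which quantity was planned for.

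Finally, the disagreement and 9% figures compare two t-tests. They do not describe the formal mixed model, which was not simulated, and they leave out the Visit 5 NPD.

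These points narrow the concern but do not remove it. The formal model still has no baseline term or contrast, and the final method is left open. Nor does pilot status answer it: the protocol calls only the secondary endpoints purely exploratory, and it sets a numerical threshold for the primary one.

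**Conclusion.** The concern holds as an ambiguity that should be closed. The current text permits an unadjusted final-value comparison, a change-score comparison or a mixed model with free baseline means, and it defers the choice to the data. None of these three uses the Visit 1 NPD efficiently.

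At an assumed SD of 5 mV, adjustment gains about 11 points of power over both simple versions at a repeat-test correlation of 0.5. It gains about 32 points over the final value at 0.8, and essentially nothing over it at 0.2 or below. The risk from leaving the choice open does not depend on a power difference: about one trial in three would give conflicting t-test verdicts under the target effect, and picking the significant one would nearly double the type I error. All these sizes rest on assumed SDs and correlations. They show what is possible and do not estimate this trial's operating characteristics.

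**What to change.** Use one definition in the primary hypothesis, the endpoint list and the analysis section: the between-arm difference in the 0 Cl-/isoproterenol NPD response at Visit 7, adjusted for the Visit 1 response. Fit it by ANCOVA, or by the planned mixed model with Visit 1 as a covariate or with arm means constrained equal at baseline. State the -4 mV as that adjusted difference. Label the unadjusted t-test descriptive. Replace the sentence that leaves the final approach to the available data with this model, fixed before unblinding.

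The cost is wording in three places and one degree of freedom. If the repeat-test correlation is very low, about 1 point of power may be lost. No visit, test or patient is added, because the Visit 1 NPD is already scheduled.

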### Intervention

- After establishing baseline parameters, patients will be started on oral losartan, 50 mg or 25 mg (based on patient's weight) daily in am for 1 week before dose will be increased to twice daily in am and pm. If participant present any relevant AE related to the study medication, at the PI discretion, the dose will not be increased to BID and participant will be withdrawn from the study. .
- Trial is randomized 1:1 to active drug and placebo (pharmacy will provide drug and placebo; randomization occurs through the biostatistics core at University of Miami).

### Measurements

1. Visits will occur for screening, baseline and then treatment according to the attached schedule.

2. Sample collection will include NPD, sweat chloride, nasal cell and nasal fluid collection, spirometry, CFQ-R, serum C-reactive protein (hsCRP), WBC (including absolute neutrophil count, % PMNs), serum alpha-SAA, calprotectin, and GM-CSF. In addition, losartan and EXP3179/3174 levels will be assessed (17,18).. Nasal airway epithelial cells will be taken by brush for mRNA expression levels of TGF- $\beta$  and LRRC26. Exacerbation assessment, defined according to the TRAFFIC/TRANSPORT studies (19) will occur during study visits and unscheduled visits if needed

### Inclusion criteria:

- CF patients homozygous for F508del and on current treatment with OrkambiTM or SymdecoTM for at least 3 months
- Age >12 years
- FEV1  $\geq$  40% of predicted

### Exclusion criteria

[figure not shown]
- When enrolling female patients
  - Not willing to adhere to strict birth control (combination of two methods)
  - Pregnancy
- History of intolerance to angiotensin receptor blockers (ARBs)
- Treatment with ACE inhibitor
- Regular use of NSAIDs or potassium supplementation, treatment with aliskiren, or on anticoagulation
- Oral corticosteroid use within 6 weeks
- Exacerbation requiring treatment within 4 weeks
- Current treatment for mycobacterial infections
- Significant hypoxemia (oxygen saturation <90% on room air and rest or use of continuous oxygen treatment), chronic respiratory failure by history (pCO2 > 45 mmHg), clinical evidence of cor pulmonale
- Untreated arterial hypertension (systolic blood pressure >140 mm Hg, diastolic blood pressure > 90 mmHg)
- Blood pressure less than 90 mm Hg systolic while standing
- Cardiac, renal (creatinine 1.5 times normal limit), hepatic (LFTs > 3x normal upper limit), neurological, psychiatric, endocrine or neoplastic diseases that are judged to interfere with participation in study
- Known renal artery stenosis
- Concomitant airway disorders other than CF, such as ABPA.
- Subjects with prior thoracic surgery

The visits are detailed in the attached table. The timeline and randomization is given in Figure 2 below.

Measures of Compliance: This will be accomplished in two ways: analysis of blood levels of losartan and the metabolites EXP3179/EXP3174; pill count (patients will bring their medication supply to the visits).

Timeline: We will start up the trial in April 2017 with database creation for data capturing. We expect to start enrollment within 3 months. We expect to enroll each year 18 patients and be able to publish the results by the end of the 3.5-year funding request.

Other issues: Efficacy and safety are addressed in the DSMB section. Data collection will occur by clinical research coordinators. Data monitoring and quality control will be provided by the Clinical Research Operations & Regulatory Support (CRORS) monitoring group at the University of Miami.

**Figure 2. Timeline and interventions.** The enrollment and interventions are depicted graphically for an easier understanding. More detailed visit procedures are provided in the attached table.

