## **STUDY DRUG: LOSARTAN**

Cozaar®, the commercial form of losartan is an FDA-approved ARB widely prescribed for treatment of hypertension, heart failure, and for renal protection in patients with diabetes. Losartan and matching placebo (25 mg or 50 mg pills/ placebo) will be compounded at each site by the research pharmacist and distributed to the subject based on the randomization table provided by the Biostatistician at University of Miami. Losartan/placebo will be given to the subjects by the PI or study coordinators free of charge. FDA has granted IND exemption for this study. The research pharmacist is responsible for maintaining accurate study drug accountability records throughout the study. Dose will be adjusted based on participant's weight at visit 1 as following: if participant's weight is  $< 55$  kg, participant will be randomized to either 25 mg or placebo. If participant's weight is  $\geq 55$  kg, participant will be randomized to either 50 mg or placebo.

Each dispensing of study drug will be documented in the subject's study records and in the drug accountability log. Subjects will return all unused study drug for drug accountability. Study drug will be destroyed at the research site as per the Institution regulations at the end of study.

Research pharmacists, UM biostatistician core and the assign unblinded monitor will be unblinded. Emergency plan for unblinding will be discussed with PI with consulting with the medical monitor and DSMB if necessary.

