Treatment with losartan (IND exemption for CF approved): Losartan is an FDA-approved ARB widely prescribed for treatment of hypertension, heart failure, and for renal protection in patients with diabetes. The doses proposed in this study are well tolerated by non-hypertensive patients without significant effect on blood pressure. The most common side effects are fatigue and dizziness. Serious adverse events that are rare include angioedema, hypotension, renal dysfunction or failure, blood dyscrasias, hepatitis, or rhabdomyolysis (clinical assessment of muscle pain). The following should lower the risks to the subjects: The first dose of medication will be administered in the clinic and the patient observed for two hours with blood pressure monitoring. Subjects with hyperkalemia, renal dysfunction, or who are taking potassium supplements will not be enrolled into the study. Participants will be given written descriptions of potential side effects and what to do. For example, mild postural hypotension can be minimized by getting up slowly and maintaining adequate hydration. Skin rashes, palpitations or other moderate or severe adverse events (interference with usual daily activities) without other clear explanation should warrant immediate cessation of treatment and notification of study personnel. There are no drug interactions between losartan and OrkambiTM. Nor are there relevant drug interactions between losartan and or SymdecoTM (by Vertex' drug interaction guidance in their 661 and later clinical trials).

Sweat chloride collection: this is a routine procedure in a CF center and uses a macroduct to collect sweat secretions stimulated by pilocarpine iontophoresis, done according to CFF and CLSI guidelines. The test is well tolerated. A small risk of complications includes mild reddening of the skin. Damage to the skin, such as blistering or burns, occurs very infrequently and this risk can be minimized by careful attention to technique.

Questionnaires, Health History and Physical Examination acquire information that is routinely collected. No significant physical risks arise from these procedures. There is always the risk of psychological distress and breach of confidentiality. In order to minimize this risk, electronic medical records are held in HIPAA compliant password-protected databases, and written information is stored in locked files or file-rooms when not attended by study personnel.

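### The exclusion list does not bar current ARB treatment, so a patient already taking losartan can be randomised; the likely dilution is small, but the gap is real and cheap to close

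*Combined protocol and SAP*

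**What the plan says.** All references are to the combined protocol and SAP.

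- **Exclusion criteria, renin-angiotensin drugs.** Two classes are barred when in use: "Treatment with ACE inhibitor", and aliskiren within the item "Regular use of NSAIDs or potassium supplementation, treatment with aliskiren, or on anticoagulation". For ARBs the only item is "History of intolerance to angiotensin receptor blockers (ARBs".
- **Exclusion criteria, blood pressure.** The hypertension item reads "Untreated arterial hypertension (systolic blood pressure >140 mm Hg, diastolic blood pressure > 90 mmHg". It does not reach a patient whose hypertension is treated.
- **Inclusion criteria.** The only medication requirement is CFTR modulator therapy. Age has a lower limit but no upper one.
- **Potential Risks.** A further enrolment restriction states: "Subjects with hyperkalemia, renal dysfunction, or who are taking potassium supplements will not be enrolled into the study". It does not mention ARBs.
- **Study Drug: Losartan.** Losartan is identified as an ARB that is "widely prescribed for treatment of hypertension, heart failure, and for renal protection in patients with diabetes".
- **Compliance** (paragraph after the exclusion list). Two measures are named: blood levels of losartan and its metabolites, and pill count.
- **Appendix 1.** Concomitant medications are recorded at Visit 1, with changes reviewed at every later contact. Losartan levels are marked at Visits 5 and 7 only.

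**The concern.** The trial asks whether adding losartan changes CFTR conductance compared with not adding it. A patient who already takes losartan can inform that contrast poorly. If allocated to active drug, the baseline NPD was measured on losartan, and little further change may follow. Such a patient adds to the denominator without adding much signal, in a trial of 36 whose withdrawals are not replaced.

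Two other things are at stake. Losartan from outside the study would appear in the blood samples meant to show adherence to study drug. A patient on any ARB who is allocated to losartan would also receive two drugs of one class, although the list takes care to keep out two related classes.

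**Working it through.** **1. Does any other text close the gap?**

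| Section | Bearing on current ARB use |
|---|---|
| Inclusion criteria | None |
| Exclusion criteria | ARB intolerance only; ACE inhibitor and aliskiren treatment barred |
| Study Drug: Losartan | Dose by weight, dispensing, unblinding; no ARB rule |
| Potential Risks | Hyperkalemia, renal dysfunction, potassium supplements; no ARB rule |
| Removal of Subjects from Study | No ARB rule |
| Appendix 1 | Medications recorded; no rule acts on the record |

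No washout or prohibited-medication list appears in the readable text. A patient with treated hypertension who takes and tolerates losartan fails no specific criterion.

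**2. The plan's own figure.** Study Design and Methods gives 36 patients, 18 per arm, and an expected difference of more than 4 mV in magnitude. The readable text gives neither the SD nor the power, so 36 cannot be reproduced. The point does not depend on it.

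**3. Dilution.** Assume that an ARB user allocated to losartan shows zero further change, and that a stable user on placebo changes like any other placebo patient.

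- One user, allocated to losartan: 4/18 = 0.22 mV; 0.22/4 = 5.6%.
- One user, averaged over 1:1 allocation: 1/2 × 4/18 = 4/36 = 0.11 mV; 0.11/4 = 2.8%. Expected difference 4 − 0.11 = 3.89 mV.
- Two users, averaged: 2 × 4/36 = 0.22 mV. Expected difference 3.78 mV.
- Two users, both allocated to losartan: 2 × 4/18 = 0.44 mV (11%).
- No users: no loss.

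If a user has a fraction r of the full response, each figure is multiplied by (1 − r), so the zero-change figures are upper bounds for r between 0 and 1.

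**4. Effect on power (illustration only).** Assume 80% or 90% power for 4 mV at two-sided 0.05 with 18 per arm. The implied SD is 4/[(1.960 + z) × √(2/18)], where z is 0.842 or 1.282, giving 4.28 mV or 3.70 mV. Holding the SD fixed:

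| ARB users among 36 | Expected difference | Power if 80% planned | Power if 90% planned |
|---|---|---|---|
| 0 | 4.00 mV | 80.0% | 90.0% |
| 1 | 3.89 mV | 77.8% | 88.3% |
| 2 | 3.78 mV | 75.4% | 86.5% |

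The numbers of users are assumptions, since the documents give no prevalence.

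**The case against.** The best case against the point is that it may never arise. Nothing in the documents shows that any F508del homozygote at these sites takes an ARB; the description of losartan as widely prescribed is not about cystic fibrosis. Cardiac, renal and endocrine disease can already lead to exclusion on the investigator's judgement, which covers part of the ground where ARBs are used. The first dose is given in clinic with two hours of blood-pressure monitoring. All of this stands and limits the likely size. None of it is a rule on ARB use.

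Four stronger readings are tempting and are not supported:

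- *A reader might infer that an ARB user on placebo biases the primary comparison.* The hypothesis is worded as a change, and the statistics section plans for paired measures. A stable user on placebo should change by about zero, as other placebo patients do.
- *A reader might take 0.22 mV per user as the expected loss.* That holds only for a user allocated to losartan; the average over allocation is half of it.
- *A reader might treat zero further change as established.* It is an assumption. It is weaker for ARBs other than losartan, because the protocol credits part of the anti-inflammatory action to a losartan metabolite. It is also uncertain for losartan users, because the study drug adds to their exposure.
- *A reader might infer that, with no baseline losartan level, prior use would go unseen.* The Visit 1 medication record would show it without an assay.

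One reservation concerns the source. A figure under the exclusion heading is not reproduced in the text reviewed. It is probably the Figure 2 timeline, whose caption closes that section, but a criterion shown there cannot be ruled out.

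**Conclusion.** The gap holds on the readable text: the criteria admit a patient already taking losartan or another ARB, and no other section prevents it. The statistical cost is modest and conditional: at most about 0.11 mV (2.8% of 4 mV) expected per enrolled user, roughly two percentage points of power under the illustrative assumptions, and zero if no user is enrolled. This rests on an analysis of change from baseline and on stable prior treatment.

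Two consequences do not depend on that arithmetic. Open-label losartan would leave the blood-level compliance measure uninterpretable in either arm, with pill count as the only remaining check; other ARBs would not have this effect. Duplicate ARB exposure is possible in the active arm, which sits badly with the list's own ACE inhibitor and aliskiren items. Those items suggest that the omission is an oversight; the documents do not say that ARB users were meant to be enrolled.

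**What to change.** Add one item to the Exclusion criteria, beside those on ACE inhibitors and aliskiren: *current treatment with any ARB, including losartan*. Leave any look-back period to the sponsor. State that eligibility on this item is checked against the concomitant medication record already taken at Visit 1.

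The cost is one protocol amendment, which the Protocol Amendments section sends to the IRBs for approval before use, and possibly a very small number of lost candidates. No visit, test or change to the sample size is needed. The amendment would not reach patients already randomised, but the same medication record would identify any ARB users among them.
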